5.6 Blinding

Participants, laboratory staff analysing samples and clinicians assessing causality of AEs will not be informed of the treatment allocation. Staff involved in delivery of the trial treatment and collecting blood samples will be aware of which vaccines/injections a participant is receiving.

Vaccines will be prepared out of sight of the participant and the blind will be maintained by either i) asking participants to look away, ii) masking the syringe with tape and iii) using syringes that as similar as possible. The success of blinding will be assessed using the Bang Blinding Index.

5.7 Unblinding

Requests to unblind on clinical grounds are not anticipated. However, if unblinding is requested on safety grounds (e.g., a participant may be unblinded if they experience anaphylaxis), this will be facilitated by contacting the coordinating centre (during normal office hours) or UHBW

pharmacy (outside normal office hours). Any such request will be fully documented including who requested the unblinding and the reason for unblinding. Unblinding will only be permitted if it is required for clinical management. Details of the trial treatment received will be sent to the attending physician.

If a suspected unexpected serious adverse reaction (SUSAR) is reported, the Sponsor will receive an unblinded report from the BTC for further reporting purposes as required by the MHRA. The CI, local PI and blinded clinicians will not be unblinded unless it is indicated on safety grounds.

Unblinding rates will be monitored throughout the trial by the trial team and by the independent Data Monitoring and Safety Committee (DMSC) established to oversee participant safety in the trial (see Section 13 for further details).

Participants will be made aware before entering the trial that they will not be told which treatment they will receive until after the trial has completed.

5.8 Research procedures: participants

Participants will be required to do, or undergo, the following tasks or investigations specifically for the trial which are also outlined in schedule of events (Table 4).

Table 4 Schedule of events

Visit	V1	V2	V3	V4	V5	V6
Timing (days)	D0	D28	D56	D84	D112	D140
Window periods (days)	-	D26-32	D56-60	D82-86	D112-116	D140-146
Eligibility	x					
Urine sample*	x		x		x	

Randomisation	x					
Vaccinations	x		x		X	X**
Bloods (serum) (COVID-19 subset)	x	x	x	x		
Bloods (serum) (Influenza subset)	x	x	x	x		
Bloods (serum) Anti-gE Ig	x		x	x		x
Blood (whole) RZV Cell- mediated immunology (CMI)	x		x	x		x
Blood (whole) exploratory immunity	x	x				
+Diary Card training	x					
Diary Card review						
Safety Review						
Quality of life survey	x		X***		X***	
Missed workdays			x		x	

* Urinary pregnancy testing for female participants of child-bearing potential only**Group 1 will receive the flu vaccine at visit 6 if in the winter vaccination season.

***Quality of life survey completed 7 days after vaccination

Volunteers interested in participating will be asked to complete an ‘expression of interest/initial screening’ questionnaire available via a public website. See section 12.3 for details of how the public will be made aware of the trial.

The ‘expression of interest/initial screening’ questionnaire will assess whether the volunteer meets the key inclusion criteria for participation (e.g. age, received their initial course (usually two doses) of COVID-19 vaccinations). If these criteria are met, they will be asked to indicate their electronic consent to proceed to more detailed screening, and for the research team to contact their GP for further clarification of medical history (if required) and confirmation of vaccination record.

5.8.1 Detailed pre-screening

This second stage includes the following elements:

- Reporting their medical history
- Review of medical history (if required, depending on responses, may be completed remotely)

Volunteers without a past medical history or drug history requiring review will proceed to a full eligibility check (section 5.8.2) once their vaccination status has been confirmed.

Volunteers will be contacted by delegated members of the research team who will obtain medical information and check medical records if needs be to confirm provisional eligibility. The volunteer will be asked to contact the trial team if there are significant changes to their health status between pre-screening and their first trial visit (if this takes place on different days).

5.8.2 Visit 1: Recruitment and administration of trial vaccine

Once confirmed as potentially eligible volunteers will be asked to:

- Confirm they understand the contents of the ZosterFluCov trial PIL (this will be available via the pre-screening website)
- Discuss the trial with a member of the research team

Provide informed consent to participate, to the PI or an appropriately trained and delegated member of the study team, if willing to do so

If consent is given the participant will undergo the following:

- Medical history review
- History directed physical examination as required
- Eligibility confirmation by PI or medically qualified doctor
- Measurement of temperature, height and weight
- Complete Quality of Life questionnaire

Following consent and collection of baseline data, the participant will be randomised. The participant will then provide a blood sample for assessment of RZV, COVID-19 and influenza vaccine immunogenicity (immunogenicity and exploratory/CMI subsets*). Then, the trial vaccines will be administered. The participant will remain at the trial site for observation for at least 15 minutes following the vaccination, in case of immediate AEs.

In group 3 only 129 participants will progress to the second and third vaccination time points required to assess C19/RZV co-administration.

5.8.3 Between visit 1 and visit 2

In the period following the first visit and the second visit approximately 4 weeks later participants will be required to:

- Complete an electronic diary card for the first 7 days. This diary card will be used to capture:
 - AEs, including their timing and severity
- Report any hospitalisation as soon as is practically possible using the emergency 24-hour telephone number provided
- Report any other urgent medical concerns using the trial centre emergency procedures

- Report any unsolicited adverse events on the electronic diary card between day 8 and day 30 after vaccination
- Complete Quality of Life questionnaire 7 days after vaccination

Diary cards will be reviewed by the local research team daily for 7 days after visit 1 and as required thereafter, and participants may be telephoned by the local research team if any entries are missed and the PI or delegated clinician if there are any concerns about reported symptoms. Participants will be provided with a ruler and thermometer to aid their reporting of AEs. Participants who do not have access to an internet connected device, will have the option to complete a paper diary. Participants will be encouraged to report any symptoms to the local research team and will be contacted by the local research team between day 4-7 to review their diary entries.

5.8.4 Visit 2: Safety review and blood sampling

At this visit, approximately 4 weeks after visit 1, participants will undergo the following:

- Safety review to assess for any serious adverse events
- Review and reconciliation of diary card data submitted
- Assessment for local and systemic adverse reactions and events and medical history since visit 1
- Provide blood sample for assessment of COVID-19, influenza vaccine immunogenicity
- Provide blood sample for exploratory immunology analysis*
- Participants in group 3 who will not be invited to continue the study will be informed and permission sought to follow up to resolution any clinically significant adverse events after the end of trial participation

5.8.5 Between visit 2 and visit 3

In the period between the second visit and the third visit approximately 4 weeks later participants will be required to:

- Report any hospitalisation as soon as is practically possible using the emergency 24-hour telephone number provided
- Report any other urgent medical concerns using the trial centre emergency procedures
- Report any unsolicited adverse events on the electronic diary card

5.8.6 Visit 3 Safety review, blood sampling and administration of trial vaccine

- Safety review to assess for any serious adverse events
- Confirm fitness to continue in study
- Provide blood sample for assessment of RZV, COVID-19, influenza vaccine immunogenicity
- Provide blood sample for assessment of RZV immunogenicity and cell-mediated immunity against RZV in CMI subset*
- Measurement of temperature
- Receive trial vaccines as per randomisation allocation

5.8.7 Between visit 3 and visit 4

- Complete an electronic diary card for the first 7 days. This diary card will be used to capture:

- AEs, including their timing and severity
- Report any hospitalisation as soon as is practically possible using the emergency 24-hour telephone number provided
- Report any other urgent medical concerns using the trial centre emergency procedures
- Report any unsolicited adverse events on the electronic diary card between day 8 and day 30 after vaccination
- Complete Quality of Life questionnaire 7 days after vaccination

5.8.8 Visit 4

At this visit, approximately 4 weeks after visit 3, participants will undergo the following:

- Safety review to assess for any serious adverse events
- Review and reconciliation of diary card data submitted
- Assessment for local and systemic adverse reactions and events and medical history since visit 3
- Provide blood sample for assessment of RZV, COVID-19 and influenza vaccine immunogenicity
- Provide blood sample for assessment of cell-mediated immunity against RZV in CMI subset*

5.8.9 Between visit 4 and visit 5

In the period between the fourth visit and the fifth visit approximately 4 weeks later participants will be required to:

- Report any hospitalisation as soon as is practically possible using the emergency 24-hour telephone number provided

- Report any other urgent medical concerns using the trial centre emergency procedures
- Report any unsolicited adverse events on the electronic diary card

5.8.10 Visit 5 Safety review, blood sampling and administration of trial vaccine

- Safety review to assess for any serious adverse events
- Review and reconciliation of diary card data submitted
- Assessment for local and systemic adverse reactions and events and medical history since visit 1
- Physical examination (if clinically indicated)
- Measurement of temperature
- Administration of trial vaccines as per randomisation
- Semi-structured interview (optional)* (See section 8 for further details)

5.8.11 Between visit 5 and visit 6

- Complete an electronic diary card for the first 7 days. This diary card will be used to capture:
 - AEs, including their timing and severity
- Report any hospitalisation as soon as is practically possible using the emergency 24-hour telephone number provided
- Report any other urgent medical concerns using the trial centre emergency procedures
- Report any unsolicited adverse events on the electronic diary card between day 8 and day 30 after vaccination
- Complete Quality of Life questionnaire 7 days after vaccination

5.8.12 Visit 6

At this visit, approximately 4 weeks after visit 5, participants will undergo the following:

- Provide blood sample for assessment of RZV vaccine immunogenicity
- Provide blood sample for assessment of cell-mediated immunity against RZV in CMI subset
- Participants randomised to group 1 will receive the flu vaccine if the visit is taking place during the winter vaccination season
- Confirm consent to follow up any clinically significant adverse events after end of participation in the study
- Semi-structured interview (optional) (See section 8 for further details)

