1.1 Trial schema

Figure 1 Trial schema

Interested volunteers complete online expression of interest questionnaire					
↓					
Pre-screening of initially eligible volunteers by recruiting site					
↓					
Time point	Group				
	1	2	3	4	5
Visit 1 Day 0	All participants: Consent, medical history and physical examination, observations (including height, weight, temperature), eligibility confirmation, randomization and vaccination				
	Blood sample: S-protein and exploratory subset T-cells	Blood sample: gE serology, CD4+ and exploratory subset T-cells	Blood sample: HAI and exploratory subset T-cells	Blood sample: HAI and gE serology and CD4+ subset	Blood sample: gE serology and CD4+ subset
	C19 + Placebo	RZV + Placebo	aQIV + placebo	RZV + aQIV	RZV + placebo
Participant completes diary for 7 days and reports any hospitalisations or concerns.					
Half of the participants in group 3 will end the study here					
Visit 2 Day 26 - 32	All participants: safety review.				
	1	2	3	4	5
	Blood sample: S-protein and exploratory subset T-cells	Blood sample: exploratory subset T-cells	Blood sample: HAI and exploratory subset T-cells	Blood sample: HAI	-
Visit 3 Day 56-60	All participants: safety review, temperature and vaccination.				
	1	2	3	4	5
	Blood sample: gE serology and CD4+ subset	Blood sample: S-protein	Blood sample: S-protein, gE serology and CD4+ subset	-	Blood sample: HAI
	RZV + Placebo	RZV + C19	C19 + RZV	RZV + placebo	RZV + aQIV
Participant completes diary for 7 days and reports any hospitalisations or concerns.					
Visit 4 Day 82-86	All participants: safety review.				
	1	2	3	4	5
	-	Blood sample: S-protein, gE serology and CD4+subset	Blood sample: S-protein	Blood sample: gE serology and CD4+ subset	Blood sample: HAI, gE serology and CD4+ subset
Visit 5 Day 112-116	All participants: safety review, temperature and vaccination*.				
	1	2	3	4	5
	-	-	-	-	-
	RZV	aQIV or placebo*	RZV	C19 or placebo*	C19 or placebo*
Participant completes diary for 7 days and reports any hospitalisations or concerns.					
Visit 6 Day 140-146	All participants: safety review.				
	1	2	3	4	5
	Blood sample: gE serology and CD4+ subset	-	Blood sample: gE serology and CD4+ subset	-	-
	aQIV*				

*these vaccinations will be given if the visit is taking place during the winter vaccination season, if not, a placebo injection will be given instead for visit 5.

2. Background & Rationale

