9.3 Samples remaining after all testing for this trial is completed

Participants will be informed that there may be leftover samples of their blood (after all testing for this trial is completed). Participants will be able to decide if they permit future use of any leftover samples.

With the participants' informed consent, any leftover serum or peripheral blood mononuclear cells will be kept for future analysis of COVID-19 and other coronavirus-related diseases or vaccine-related responses and other future research (exploratory immunology), including genotypic testing of genetic polymorphisms potentially relevant to vaccine immunogenicity.

If a participant elects not to permit this, all that participants' leftover samples will be discarded at the end of the trial.

Samples that are to be stored for future research will be transferred to a licenced Research Tissue Bank.

10. Definition of end of trial

The definition of the end of the trial is the date when all participants have completed visit 6, or are lost to follow-up, all samples have been analysed, the database has been locked and all data queries have been resolved.

The end of the trial for an individual patient is defined as completion of visit 6 or loss to follow-up.

11. Safety data collection and reporting

Participants will be asked to complete an electronic diary of solicited local (pain, redness, and swelling at injection site) and systemic (fatigue, fever GI symptoms (nausea, vomiting, diarrhoea and/or abdominal pain) headache, myalgia, shivering) AEs for 7 days after each vaccination.

Participants will be asked to record unsolicited AEs, up to 30 days after vaccination. Participants would be counselled with regard to expected side effects during the consent process and in the diary training. Leaflets about side effects would also be provided for participants.

Serious adverse events and adverse events of special interest (pIMDs) should be collected until the study end.

Safety monitoring

Safety monitoring would be continuous throughout the whole study and performed in real-time for the first 7 days after vaccination in the following ways:

- Participants would be required to complete electronic diary cards that would be reviewed in real time by trial physicians and the trial coordination team. All events will be reviewed, and reports of any grade 3 or above will trigger an alert to the relevant teams.

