13.5 Frequency of analyses

The analysis of the primary safety outcome will take place when all recruited participants have submitted 7-day diary information, that this has been reviewed at visit 6, the data relating to the 7-day outcomes are checked and complete and that element of the database can be locked.

Analyses of other outcomes will take place when the trial is complete, and the database is locked.

14. Trial management

University Hospitals Bristol and Weston NHS Foundation Trust will act as Sponsor. The BTC will act as the coordinating centre for the trial. Responsibility for running the ZosterFluCov trial will be established via a collaboration agreement with the University of Bristol. Agreements between the Sponsor and participating centres will be required, as well as standard site initiation documents, before recruitment commences. Appropriate contractual arrangements will also be put in place with other third parties.

The trial will be conducted in accordance with GCP guidelines, the Medicines for Human Use (Clinical Trials) Regulations 2004 and subsequent amendments, the Data Protection Act and the UK Policy Framework for Health and Social Care Research. The trial will be registered on an open access clinical trial database (ISRCTN).

Clinical trial documents will be archived and held by the Sponsor for 15 years after trial closure in accordance with the standard operating procedures of the Sponsor and in compliance with the principles of GCP.

The trial will be managed by the Chief Investigator (CI), with mentoring and support from senior members of the research team who will provide experience of implementing large scale clinical trials, and the Trial Managers, with full support from the wider BTC, which is a UK Clinical Research Collaboration registered clinical trial unit (UKCRC Reg. No 70). The BTC has an

established track record of designing, conducting, managing and reporting multi-centre clinical trials.

The CI and coordinating centre team will work with the co-applicants to prepare the final protocol and submit the REC, MHRA and associated Health Research Authority (HRA) applications. The coordinating centre will prepare the trial documents, provide the randomisation service and design and implement the data management system.

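### The visit 6 task list omits the safety review that the schema and section 13.5 place there, and visit 6 can end participation up to 6 days before the 30-day unsolicited-AE window closes for half of the second RZV doses given alone

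*Protocol*

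**What the plan says.** Section 5.8.12 introduces visit 6 with "At this visit, approximately 4 weeks after visit 5, participants will undergo the following". The list covers blood for RZV and cell-mediated immunity, the flu vaccine for Group 1 in season, consent to follow clinically significant events after participation, and an optional interview.

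The lists for visit 2 (5.8.4) and visit 4 (5.8.8) each contain an SAE review, reconciliation of the submitted diary, and an assessment of reactions and events since the last dose. At visit 4 the last item reads "Assessment for local and systemic adverse reactions and events and medical history since visit 3". Visit 5 (5.8.10) carries the same three kinds of item.

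Two other places put the review at visit 6. The visit 6 row of the schema (1.1) says "All participants: safety review". Section 13.5 holds the primary safety analysis until all participants have "submitted 7-day diary information, that this has been reviewed at visit 6".

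On timing, the schema gives "Visit 5 Day 112-116" and "Visit 6 Day 140-146". Section 11 states "Participants will be asked to record unsolicited AEs, up to 30 days after vaccination", and 5.8.11 places the day 8 to day 30 reporting after the visit 5 dose under the heading for the period between visits 5 and 6. Section 10 states "The end of the trial for an individual patient is defined as completion of visit 6 or loss to follow-up".

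**The concern.** There are two separate defects.

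The first is a contradiction. The step on which 13.5 makes the primary safety analysis depend is absent from the task list of the visit where it is meant to happen. A site working from 5.8.12 alone would not carry it out, and no later visit exists to recover it.

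The second is a window that the schedule cannot always complete, and it affects the compared exposures unequally. Visit 5 is when Groups 1 and 3 receive their second RZV dose alone. All co-administered second doses (Groups 2 and 5) are given at day 56 and are followed by a further visit well past day 30. Key secondary objective 14 compares unsolicited AEs to 30 days after RZV alone with those after co-administration. If collection stops at visit 6, part of the RZV-alone comparator is observed for less time. Fewer events would then be counted there, and co-administration would look slightly worse than it should.

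**Working it through.** **Task lists side by side**

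| Item | Visit 2 (5.8.4) | Visit 4 (5.8.8) | Visit 6 (5.8.12) | Visit 6 elsewhere |
|---|---|---|---|---|
| Safety/SAE review | listed | listed | not listed | schema: safety review for all |
| Diary reconciliation | listed | listed | not listed | 13.5: 7-day diaries reviewed at visit 6 |
| Reactions and events since last dose | listed | listed | not listed | not named |

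The diary-review and safety-review rows of Table 4 read as blank for every visit in the available text. That may be a conversion fault, so they are not used as evidence either way.

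**Intervals between visits**

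Inputs (schema and Table 4): visit 3 D56-60, visit 4 D82-86, visit 5 D112-116, visit 6 D140-146.

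- The plan's own figure is about 4 weeks from visit 5 to visit 6. Nominal days give 140 − 112 = 28, which reproduces it.
- Shortest visit 5 to visit 6: 140 − 116 = 24 days. Longest: 146 − 112 = 34 days.
- Shortfall against day 30: 30 − 28 = 2 days on target, 30 − 24 = 6 days at the early limit, and none when the gap is 30 days or more.
- There are 5 × 7 = 35 in-window day pairs. For visit 5 on D112, 113, 114, 115 and 116, the visit 6 days giving a gap under 30 number 2, 3, 4, 5 and 6, which total 20 (57%). This counts pairs and does not forecast attendance.
- Day-56 doses: visit 4 follows after 82 − 60 = 22 to 86 − 56 = 30 days, so it too can precede day 30. Visit 5 then follows after 112 − 60 = 52 to 116 − 56 = 60 days, so the 30-day window always closes before a further visit.
- Solicited reactions: the 7-day diary closes at least 24 − 7 = 17 days before the earliest visit 6.

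**Doses affected** (planned numbers from the synopsis; schedule from Table 3)

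- Second RZV alone: Group 1, 120 (D112); Group 3, 120 continuing (D112); Group 4, 240 (D56). Total 480, of which 120 + 120 = 240 are at visit 5.
- Second RZV co-administered: Group 2, 120 (D56); Group 5, 240 (D56). Total 360, of which 0 are at visit 5.
- Section 5.8.2 gives 129 continuing in Group 3, against 120 in the synopsis. With 129 the count is 249 of 489, still about half.

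**Size if collection stops at visit 6**

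- Per affected dose: 2/30 = 6.7% of the window on target, and 6/30 = 20% at the early limit.
- Over all RZV-alone second doses: (240 × 2)/(480 × 30) = 3.3% of planned observation days if everyone is on target, and (240 × 6)/(480 × 30) = 10% if everyone is at the early limit. For co-administered second doses it is 0%.

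**The case against.** A reader might infer that solicited, unsolicited and serious events after the visit 5 dose are all under-collected in the RZV-alone control, and that the safety comparison is therefore biased. The documents do not support this.

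- A review at visit 6 is planned: the schema and 13.5 both say so. The 5.8 lists are also not exhaustive. Table 4 has urine tests and diary training that 5.8.2, 5.8.6 and 5.8.10 do not mention. Omission from 5.8.12 therefore does not show that the review will not happen.
- Solicited reactions after visit 5 are recorded in a 7-day diary (5.8.11). Under section 11 this is reviewed in real time, with alerts at grade 3 or above and contact with non-completers within 48 hours.
- SAEs are collected to visit 6 (11.3), sites report them within 24 hours of awareness (11.4), and participants report hospitalisations by telephone.
- Group 4's 240 RZV-alone second doses are handled exactly like the co-administered ones, so only half of that comparator is exposed.
- Section 5.8.11 still asks for reports to day 30, and no passage closes the e-diary at visit 6. The 6-day shortfall is one extreme pair of 35, and 15 pairs reach day 30.

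All of this stands, and it limits the point to its narrow form. It does not remove it. That the review is required elsewhere is the reason to correct 5.8.12. Real-time review covers only the first 7 days, so days 8 to 30 rest on self-report and visit reconciliation. The day-30 instruction sits under a between-visits heading that the on-target schedule cannot satisfy, and nothing says who reviews entries made after participation ends. The 5.8.12 consent item lets known events be followed; it does not detect new ones.

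**Conclusion.** The point holds in two limited parts.

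First, 5.8.12 contradicts the schema and 13.5 on what is done at visit 6. Followed alone, it leaves out the review on which the primary safety analysis depends.

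Second, the 30-day unsolicited-AE window can be cut by up to 6 days (2 on target) for 240 of 480 planned RZV-alone second doses and for none of the 360 co-administered ones. This rests on visits being held within their windows and on collection stopping when participation ends at visit 6, which the protocol implies but does not state. If entries continue to day 30 and are reviewed, the shortfall disappears.

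The outcome affected is secondary, and the protocol plans only descriptive analysis of safety outcomes. The dose counts show where the shortfall falls; they do not estimate events missed. The 7-day co-primary safety outcome is untouched by the window.

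**What to change.** 1. Add to 5.8.12 the three items from 5.8.8, referring to visit 5: SAE review, reconciliation of the diary, and assessment of reactions, events and medical history since that visit. The section then agrees with the schema and 13.5. Check that the diary-review and safety-review rows of Table 4 mark visit 6.
2. State that unsolicited-AE diary collection runs to the later of visit 6 and day 30 after the visit 5 dose, that the site reviews entries made after visit 6, and that section 10 allows for this. Record event dates, because Group 1 may receive aQIV at visit 6 and late entries could follow either injection.

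The cost is protocol wording, up to 6 more e-diary days per participant and review of any late entries, plus a visit 6 safety page like visit 4's if none exists. No visit is added.

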5.5 Randomisation

Participants will be randomised in a 1:1:2:2:2 ratio to one of five vaccine groups (Table 3).

Randomisation will be performed after informed consent has been documented and eligibility confirmed by the Principal Investigator (PI) or a delegated medically qualified doctor.

Randomisation will be performed using a secure internet-based randomisation system ensuring allocation concealment by a member of the local research team. Masking of group allocation will be applied to participants, clinicians making safety assessments and laboratory staff analysing samples. Staff administering vaccines, collecting blood samples, and performing subsequent study visits will be aware of what they are giving but not involved in subsequent observations or interactions with study subjects.

Table 3 Vaccine groups

Groups	D0	D56	D112
1 **	C19/P	RZV/P	RZV
2	RZV/P	RZV/C19	aQIV or P*
3	aQIV/P	C19/RZV	RZV
4	RZV/aQIV	RZV/P	C19 or P*
5	RZV/P	RZV/aQIV	C19 or P*

P: placebo

**if in winter vaccination season aQIV/ C19 will be given*

***Group 1 will receive aQIV at visit 6 if in winter vaccination season (day 140)*

The allocation will be computer-generated, and randomisation will be stratified by age (50 to 64 years, 65 to 70 years, 71 to 74 years, and 75 years and over) and centre to ensure distribution of age groups between the vaccine groups, by an independent BTC statistician, not involved in the trial, before recruitment begins.

All injections will be administered intramuscularly. When a vaccine is given alongside placebo, the vaccine will be administered in the non-dominant arm. When vaccines are co-administered RZV will be administered into the non-dominant arm and C19 vaccine or aQIV in the dominant arm.

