11.3 Period for recording adverse events

Data on serious adverse events, will be collected for the period the participant is taking part in the trial, i.e., from visit 1 to visit 6.

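### Group 1's in-season aQIV dose at visit 6 falls where participation and SAE collection end, so the post-vaccination AE recording required by Section 11 is not scheduled for it

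*Protocol*

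**What the plan says.** **The dose.** Section 5.8.12 provides: "Participants randomised to group 1 will receive the flu vaccine if the visit is taking place during the winter vaccination season". The Table 4 footnote agrees: "Group 1 will receive the flu vaccine at visit 6 if in the winter vaccination season". The Table 3 footnote places the same dose at day 140 and names it as aQIV, and the schema in Section 1.1 also shows it. The schema footnote offers a placebo alternative only for visit 5 ("if not, a placebo injection will be given instead for visit 5"), so outside the season Group 1 receives no injection at visit 6. Sections 6.1 and 16.6 class influenza vaccine as an investigational product and exempt no dose.

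**The recording required.** Section 11 asks for a diary of solicited local and systemic "AEs for 7 days after each vaccination". It adds: "Participants will be asked to record unsolicited AEs, up to 30 days after vaccination". SAEs and events of special interest (pIMDs) are to be collected up to study end.

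**The end of observation.** Section 10: "The end of the trial for an individual patient is defined as completion of visit 6 or loss to follow-up". Section 11.3 says that SAE data are "collected for the period the participant is taking part in the trial, i.e., from visit 1 to visit 6". Section 6.10 closes the treatment period one month after visit 5, and Section 12.5 gives five months of follow-up. The diary instructions between visits stop at Section 5.8.11, which covers visit 5 to visit 6.

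**The concern.** A site cannot satisfy Section 11 for the visit 6 dose while following Sections 10 and 11.3. Section 11 calls for a diary and a month of event recording after vaccination, but the participant has left the trial once the visit is complete. A solicited reaction, an unsolicited event or an SAE that begins after the dose would reach the trial only if the participant or the GP volunteered it, and a new SAE would lie outside the stated collection period.

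At stake is the follow-up of people given an investigational product under the trial's authorisation, and the completeness of safety reporting for that dose.

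**Working it through.** The protocol gives no figure to reproduce. The check is a cross-reading of the schedule with day arithmetic.

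**Inputs**
- Visit 5 window D112-116 and visit 6 window D140-146 (Table 4).
- Required recording after vaccination: 7 days solicited, up to 30 days unsolicited (Section 11).
- Individual end of trial and end of SAE collection: visit 6 (Sections 10 and 11.3).
- Group 1 size: 120 (Section 13.1). Loss to follow-up below 5% (Section 12.6); planning dropout 10% (Section 13.1). Recruitment period 6 months (Section 12.2).

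**Step 1. Recording due after a visit 6 dose**
- Diary: 140 + 7 = D147 to 146 + 7 = D153.
- Unsolicited events: 140 + 30 = D170 to 146 + 30 = D176.

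**Step 2. Recording scheduled after visit 6**
- No visit, call, diary or questionnaire appears after visit 6 in Section 5.8 or Table 4. Coverage is 0 of 7 diary days and 0 of 30 recording days.
- Events of special interest and pIMDs run to study end. The synopsis row on days off work equates study end with 140 days, the nominal day of the dose itself.

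**Step 3. Comparison with other aQIV doses**
- Group 2, in season, receives aQIV at visit 5. Section 5.8.11 gives that dose the 7-day diary and day 8-30 recording. The interval to visit 6 is 140 - 116 = 24 to 146 - 112 = 34 days, nominally 140 - 112 = 28.
- Group 3 participants who leave early have aQIV on day 0, a diary, and a review at visit 2 on D26-32.
- Among the scheduled trial vaccinations, only the Group 1 visit 6 dose has no scheduled follow-up at all.

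**Step 4. Number affected**
- Affected = 120 × retention × share of Group 1 reaching visit 6 in season. The share is not given, so the range is 0 to 120.
- Share 1: 120; with 5% loss 120 × 0.95 = 114; with 10% loss 120 × 0.90 = 108.
- Share one half (assumption): 60, 57 or 54.
- Calendar illustration (assumptions: season September to March, even accrual from 1 September, no loss). Reaching D140 by 31 March requires enrolment by about 11 November, which is 72 of 181 recruitment days. 72/181 = 40%, and 0.40 × 120 = 48.
- Reaching 120 requires the whole six-month spread of visit 6 dates to fall in season.

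**The case against.** The strongest reply is that this dose is not one the trial evaluates. The synopsis describes three vaccination time points. The solicited and unsolicited event outcomes concern RZV doses at days 0, 56 and 112, and Section 6.10 ends treatment a month after visit 5. The visit 6 aQIV is a single authorised vaccine, given alone, at the visit of Group 1's last scheduled blood sample. The amendment log gives the aim of the schedule change: every participant should receive both C19 and influenza vaccine. On this view it is a catch-up dose and the issue is one of drafting.

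It stands that no listed comparison uses the dose. It does not stand that the dose lies outside Section 11. Sections 6.1 and 16.6 make the vaccine an investigational product without exception, Table 4 marks visit 6 in its vaccinations row, and the diary rule covers every vaccination. Nothing in the protocol calls the dose routine care.

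A reader might infer that the dose is wholly unmonitored. That goes too far. Section 11 provides a 24-hour telephone number, GP notification and a study card, and Section 5.8.12 confirms consent to follow up clinically significant events after participation ends. These routes are passive: they set no diary, contact or window, and they rely on someone volunteering the event.

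A reader might also infer that Section 11.3 cuts off events of special interest and pIMDs. It does not, because it concerns SAEs only. The rule for the others is collection to study end in Section 11. That term is open to two readings, since Section 10 also defines an overall trial end, although the synopsis favours 140 days. On either reading, no scheduled contact would find them.

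**Conclusion.** The conflict is real and rests on the protocol's text alone. For Group 1 participants vaccinated at visit 6, the solicited and unsolicited recording that Section 11 requires cannot be carried out within the participation period the protocol defines, and SAE collection stops at the visit where the dose is given.

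The number affected is an unknown part of 120. A reader might take 120 as the expected figure, but it is a ceiling, probably well above the true number with six months of recruitment. The illustration of 48 depends on an assumed season and start date and is not an estimate from the documents.

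A reader might also infer that the safety comparison or the trial's conclusions are compromised. The documents do not support that: the dose comes after Group 1's RZV doses and their 7-day diaries, and no co-primary outcome, success criterion or RZV comparison uses it. This is a participant-safety gap that should be closed because closing it is cheap.

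**What to change.** For Group 1 participants vaccinated at visit 6, and for no others:

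- Schedule the existing 7-day electronic diary, and one telephone contact 30 days after the dose covering unsolicited AEs, SAEs, and events of special interest including pIMDs.
- Amend Sections 5.8.12, 6.10, 10, 11.3 and 12.5 so that the end point reads: *visit 6, or, for participants vaccinated at visit 6, 30 days after that dose*. A general rule of 30 days after the last vaccination would be too broad: 112 + 30 = D142 already passes the nominal D140 visit and would extend participation for nearly everyone.
- Report events after visit 6 separately. The extension adds 30/140 = 21% to nominal observation in part of one group, and pooling those events would make the between-group observation periods unequal.

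The cost is one diary and one call per vaccinated Group 1 participant, at most 120 of each, plus a protocol amendment with the approvals in Sections 15.1, 16.1 and 16.2. Sample size and primary analysis do not change.

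Relabelling the dose as routine care outside the trial would remove the textual conflict, but participants would have exactly the follow-up they have now. It is not an equivalent fix.
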